8.9. Supporting Analyses

The supporting efficacy analyses will include:

- Once data are complete, all primary and secondary outcome measures will be assessed at 12 months and compared to baseline within the Treatment group. The analysis will also explore correlation of outcomes to amount of stimulation delivered.

a Cui, L., Hung, H. M., & Wang, S. J. (1999). Modification of sample size in group sequential clinical trials. *Biometrics*, 55, 853–857. doi:10.1111/j.0006-341X.1999.00853.x

Note: For all supporting analyses, amount of stimulation delivered will be defined as the number of minutes stimulation was delivered divided by the number of minutes that stimulation could have been delivered.

- In the Crossover Group, outcome measures will be assessed at the Outcome Post Crossover Visit for all Subjects who met the inclusion criteria for low back pain at the Primary Endpoint Assessment Visit (i.e.: prior to Crossover) (Prior week average Low Back Pain, VAS of ≥ 6.0 cm and ≤ 9.0 cm (on a 10cm scale)) and inclusion criterion for ODI (Oswestry Disability Index score $\geq 21\%$ and $\leq 60\%$). The analysis will also explore correlation of outcomes to amount of stimulation delivered.
- Comparison of daily average VAS averaged over the prior 7 days of Journal entry with the single point VAS of recollection of prior 7 days of average pain.
- Comparison of EQ-5D VAS between Treatment and Control groups at each visit at which EQ-5D is recorded through 12 months.
- For the both the Treatment and Control groups, a cumulative proportion of responder analysis, so that the entire distribution of treatment response is depicted in a graph of the proportion of responders for all percentages of low back pain VAS reduction from 0% to 100%. In this manner, the number of Subjects with $\geq 50\%$ low back pain VAS improvement can be determined, for example. The analysis will also be performed for the responder analysis of ODI.
- Subject Global Impression of Change at 12 months: The analysis will explore correlation of outcomes to amount of stimulation delivered.
- Treatment satisfaction questionnaire at 12 months: The analysis will explore correlation of outcomes to amount of stimulation delivered.
- Clinical Global Impression – Global Improvement (clinician assessment) at 12 months: The analysis will also explore correlation of outcomes to amount of stimulation delivered.
- Change in opioids used for treatment of low back pain from baseline to 12 months. The analysis will also explore correlation of outcomes to amount of stimulation delivered.

Additional, ad hoc exploratory analyses may also be conducted.

Note that the supporting analyses may be incomplete at the time of PMA submission since not all Subjects may have reached 12 months post-randomization.

8.10. Health Economics

Cost-effectiveness of ReActiv8 therapy, extrapolated to the lifetime of the device, will be measured. Key economic outcome measures to be recorded will be:

- Change in work status at all visits.
- Change in consumption of medications taken for low back pain at all visits compared to Baseline. Note that an analysis may be performed of different categories of medications including for example opioids, muscle relaxants and anti-depressants.
- Assessment of health care utilization (office visits, hospital visits, emergency room visits, and other therapies such as physical therapy) at all visits.

Note that both the Treatment and Control group Subjects are required to keep medications constant from randomization until the Primary Endpoint Assessment Visit, and other health care utilization will be as per the protocol (e.g.: no additional therapies).

Following the Primary Endpoint Assessment Visit, all Subjects will be permitted to adjust medications and to use other health care resources. For the Crossover Group, this may yield some information on how Subjects will adjust medications during the treatment phase.

Note that completion of the Health Economics assessments is likely to be incomplete at the time of PMA submission for ReActiv8, since not all Subjects will have reached the 12 month point at that time.

8.11. Subgroup Analyses and Predictors of Response

The primary efficacy endpoint will be analyzed in the subgroups defined below to demonstrate consistency of treatment effect. A logistic regression model will be used to test the interaction of randomization assignment and subgroup/covariate. Subgroups to be analyzed will include, at a minimum:

- Gender
- Age (as both a continuous variable and grouped in ranges)
- Ethnicity
- Baseline VAS
- BMI (as both a continuous variable and grouped in ranges)
- Duration of work status adversely affected by CLBP

Multivariable analysis to explore predictors of response will be conducted in the Treatment group Subjects. Univariable regression models with covariates as defined below will be analyzed to determine predictors of response. All covariates with an association with response ($p < 0.20$) will be included in a multivariable logistic regression model.

- Duration of back pain (as both a continuous variable and grouped in ranges)
- Baseline ODI (as both a continuous variable and grouped in ranges)
- Baseline EQ5D (as both a continuous variable and grouped in ranges)
- Baseline VAS (as both a continuous variable and grouped in ranges)
- Baseline opioid use
- Age
- Gender
- BMI
- Compliance with stimulation (the number of minutes that stimulation was actually delivered divided by the number of minutes that could have been delivered)

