6.1. Sample Size Estimate

The sample size for the study is determined under the following assumptions for the primary efficacy endpoint:

- Minimum power of 80%
- Type I error of 5%
- Assumed primary efficacy success in Treatment group: 50%
- Assumed primary efficacy success in Control group: 25%

Under the above assumptions, a minimum of 116 evaluable Subjects is required in order to demonstrate superiority of the ReActiv8 treatment. The total sample size is increased by 10% to 128 to allow for attrition. The total sample size may be increased, but not decreased, at the time of the planned interim analysis to adjust for updates to the planning assumptions.

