6.2. Level of Power and Significance

All tests of significance will be performed at the two-sided 0.05 significance level. The hypotheses associated with the first five secondary efficacy objectives will be tested using the Hochberg multiple comparison adjustment in the event the primary efficacy objective is met.

7. Data Structure and Handling

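### SAP 8.11 aims to show that the treatment effect is consistent across subgroups, but a non-significant interaction test in a trial sized only for the overall effect cannot show that (minor)

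*SAP*

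**What the plan says.** SAP 8.11 gives the purpose and the method in two consecutive sentences. The responder outcome "will be analyzed in the subgroups defined below to demonstrate consistency of treatment effect. A logistic regression model will be used to test the interaction", namely that between randomised arm and each subgroup variable. The list covers, at a minimum, gender, age, ethnicity, baseline VAS, BMI and duration of affected work status. Age and BMI are each to be examined both as continuous variables and in ranges.

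The section gives no significance level of its own, so the general rule of SAP 6.2 applies: "All tests of significance will be performed at the two-sided 0.05 significance level". It gives no cut-points, expected subgroup sizes, interaction power, multiplicity rule or margin, and it does not say how a non-significant interaction is to be read.

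The sample size in SAP 6.1 rests on the overall comparison alone. With 50% responders on Treatment, 25% on Control, 80% power and 5% type I error, "a minimum of 116 evaluable Subjects is required in order to demonstrate superiority of the ReActiv8 treatment". SAP 8.7 allows an increase to at most 2 x 116.

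Two other sections bear on the point. SAP 8.1 has binary outcomes shown as proportions with 95% confidence limits, and SAP 8.5.1 presents the difference in responder proportions with 95% limits.

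**The concern.** Consistency of effect is a claim that subgroup effects do not differ by an amount that matters. The interaction test has no difference in effect as its null hypothesis, so a significant result contradicts the claim, while a non-significant result only fails to contradict it. Demonstrating consistency would need a bound on the between-subgroup difference, and SAP 8.11 specifies neither a margin nor an interval for that difference.

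A trial sized for a main effect usually has much less information on an interaction. A non-significant result could then be carried into a report as evidence that a permanent implant works equally well in, say, both sexes or all BMI ranges, when the data would also fit no benefit in one of them.

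The opposite error is possible too. Several interactions are tested with no multiplicity adjustment, so a lone p<0.05 could be over-read as a real difference.

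**Working it through.** **Inputs.** From SAP 6.1: 50% vs 25%, 116 evaluable. From SAP 5.1: 1:1 allocation, so 58 per arm. From SAP 6.2: two-sided 0.05. From SAP 8.7: a cap of 232. The documents give no subgroup sizes or subgroup effects, so both are assumptions below.

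**1. The plan's own figure.** With the pooled-variance formula and mean proportion 0.375:

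n per arm = [1.96 × √(2 × 0.375 × 0.625) + 0.8416 × √(0.25 + 0.1875)]² / 0.25² = 57.7, rounded up to 58, or 116 in total.

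This matches SAP 6.1. Power for the overall comparison at 58 per arm is 80.2%.

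**2. Interaction test: formula.** The logistic interaction term for two subgroups is the difference of two log odds ratios. Its variance is the sum of 1/[n p (1−p)] over the four arm-by-subgroup cells. Power is approximately Φ(δ/SE − 1.96).

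**3. Scenario 1: the benefiting subgroup has the planned 50% vs 25%, the other 25% vs 25%.** At an even split each cell holds 29 Subjects.

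- SE = √[1/(29 × 0.25) + 3/(29 × 0.1875)] = 0.83
- δ = log 3 = 1.10, and δ/SE = 1.32
- Power is about 26%, so the miss rate is about 74%.

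**4. Scenario 2: the overall rates stay at 50% vs 25%, with all benefit in one subgroup.** If a fraction f gains nothing, the others must respond at (0.50 − 0.25f)/(1 − f) on Treatment. At f = 0.5 this is 75%.

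- SE = √[4/(29 × 0.1875)] = 0.86
- δ = log 9 = 2.20, and δ/SE = 2.56
- Power is about 73%, so the miss rate is about 27%.

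**5. Other splits, by the same formula (miss rate).**

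| Share with no benefit | Scenario 1, N=116 | Scenario 2, N=116 | Scenario 1, N=232 | Scenario 2, N=232 |
|---|---|---|---|---|
| 50% | 74% | 27% | 54% | 5% |
| 40% | 75% | 45% | 56% | 16% |
| 30% | 78% | 62% | 61% | 35% |
| 20% | 82% | 75% | 69% | 56% |

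Simulated likelihood-ratio and Wald tests agreed closely. At N=116 they ran from 73% to 85% in Scenario 1 and from 26% to 78% in Scenario 2. For 80% interaction power at an even split, about 524 Subjects are needed in Scenario 1 and about 140 in Scenario 2.

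**6. Continuous covariates.** For age or BMI entered as a continuous term, power depends on a slope that the SAP does not state. Simulated power at 116 was about 66% if the benefit vanishes 1 SD below the mean and about 25% if it vanishes 2 SD below.

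**7. A check that assumes no heterogeneity.** Let the effect be 50% vs 25% in both halves. On the risk-difference scale:

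- SE of the between-subgroup difference in effect = √[2 × (0.25 + 0.1875)/29] = 0.174
- 95% half-width = 1.96 × 0.174 = 0.34, or ±34 points
- At 232 Subjects (58 per cell): SE = 0.123, half-width ±24 points.

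At 116 Subjects, an observed interaction of exactly zero would still be compatible with subgroup effects that differ by more than the whole planned 25 points. At the cap, the limits are about as wide as the planned benefit.

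**8. False alarms.** With a truly homogeneous effect and six independent tests, at least one p<0.05 occurs with probability 1 − 0.95⁶ = 26%, before counting the second forms of age and BMI. Independence is an assumption.

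**The case against.** **The decision rule is not in the SAP.** A reader might infer that a non-significant interaction will be reported as proof that the device works alike in everyone. SAP 8.11 does not say so; it sets no rule for declaring either consistency or inconsistency. This objection stands, and the supportable statement is that the result could be misread. The risk is not remote, however. For sites, SAP 7.4 does draw a conclusion from non-rejection, treating data as poolable when p is at least 0.15.

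**The miss rate depends on the scenario.** A reader might also infer that these tests generally miss a no-benefit subgroup 70–80% of the time. They do not. That range comes from Scenario 1, and at an even split with the planned overall effect kept, the test detects the difference about 73% of the time. Scenario 1 at an even split also means 37.5% vs 25% overall, with only about 30% power for the primary endpoint, so such a trial would usually have no efficacy claim to generalise. Among those that do succeed, the miss rate is still about 75%. The objection limits the size of the problem. It does not touch step 7, which assumes no heterogeneity at all.

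**Intervals are partly planned already.** Read with SAP 8.1 and 8.5.1, analysing the primary endpoint in subgroups can fairly be taken to include within-subgroup estimates with limits. This stands. What is missing is an interval on the between-subgroup difference and a rule for interpretation.

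**Nothing turns on it.** Trial success rests on the primary endpoint alone (Protocol 4.7.1.1, SAP 8.5.1). This stands and sets the severity.

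**Conclusion.** The concern holds in a limited form. SAP 8.11 states an aim that its named test cannot deliver at the planned size. The logical point needs no assumption about subgroups: failing to reject equal effects does not demonstrate equal effects.

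The size does rest on assumptions. For two-group splits at 116 Subjects, the miss rate runs from about 74% to 82% if the benefiting Subjects gain only the planned 25 points, and from about 27% to 75% if the overall effect is held at 25 points, as the no-benefit share falls from 50% to 20%. No single figure covers the whole list of subgroups, and for continuous age and BMI the slope is unstated. The most robust figure is the half-width of about 34 points at an even split and equal effects (about 24 at 232 Subjects), against a planned benefit of 25.

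The documents do not support saying that the plan will declare consistency wrongly, only that its wording leaves room for it. Severity is minor.

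**What to change.** In SAP 8.11:

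1. Change the stated purpose from demonstrating consistency to *describing the treatment effect across subgroups*.
2. For each subgroup, report the Treatment-minus-Control difference in responder proportions with 95% limits, in line with SAP 8.1 and 8.5.1. Add the between-subgroup difference in that effect with 95% limits. One forest plot can carry both.
3. State that a non-significant interaction is not evidence of consistency, and that isolated interactions with p<0.05 are exploratory because they are not adjusted for multiplicity.

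The cost is a change of SAP wording and one display from data already collected. No change to sample size or alpha is needed. The sponsor gives up the consistency claim, which a trial of this size is not designed to support.
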